#### **8.5.8.2 Laboratory data**

All continuous laboratory parameters will be summarized by absolute value at each visit by treatment group, together with the corresponding changes from baseline, in both primary populations. The summary statistics presented will be the minimum, 1st quartile, median, 3rd quartile, maximum, mean and SD. Mean changes from baseline over time will also be plotted by treatment group.

AstraZeneca defined extended reference ranges will be used for the identification of individual clinically important abnormalities, and a shift table will be produced for each laboratory parameter to display low, normal, high, and missing values. The shift tables will present baseline and maximum/minimum on-treatment value, as applicable for each parameter.

Shift plots showing each individual subject's laboratory value at baseline and at maximum/minimum will be produced for each continuous laboratory variable. If any laboratory variables show any unusual features (high or low values or a general shift in the data points) at other time points then shift plots of these data may be produced. A diagonal line indicating no change, and horizontal and vertical reference lines indicating the limits of the AstraZeneca defined reference ranges will also be displayed on the shift plots.

Data for subjects who have treatment-emergent changes outside the predefined criteria will be presented. This data presentation will include all visits for this subset of subjects.

The frequency of changes with respect to normal ranges between baseline and each post-treatment time point will be tabulated. Frequencies of clinically noteworthy values (using AstraZeneca defined reference ranges) occurring during the clinical study will also be given.

In order to identify potential Hy's Law cases, maximum post baseline total bilirubin will be plotted against maximum post baseline ALT, expressed as multiples of ULN. This plot will be repeated to show maximum post baseline total bilirubin against maximum post baseline AST, expressed as multiples of ULN. These plots will be produced on a log scale and reference lines will be included at 2xULN for total bilirubin and at 3xULN for ALT/AST.

For all subjects who meet the biochemical criteria for Hy's law (potential Hy's Law), a Subject Safety Narrative will be produced, and the relevant laboratory parameters will be tabulated showing all visits for these subjects. Subjects with elevated ALT or AST, and elevated total bilirubin, at any time may be explored further graphically using individual subject profile plots.

For urinalysis data, a shift table will be generated to present changes from baseline to EOT. The number of subjects with treatment-emergent changes will also be summarized. Here, treatment-emergent changes are defined as None/Trace at baseline to Positive, at any visit after baseline.

Any data outside the AstraZeneca normal and extended reference ranges will be explicitly noted on the listings that are produced.

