| Concomitant
medications                      | X               | X               | X                  | X                                | X  | X  | X  | X   | X   | X   | X   | X   | X   | X   | X   | X   | X   | X   | X   | X   | X   | X   | X   | X   | X                 | X   | X   | X   | X   |     |     |     |     |
| Blood sample
for perostin                    |                 | X               | X                  |                                  |    |    |    |     |     |     |     |     |     |     |     |     |     |     |     |     |     |     |     |     |                   |     |     |     |     |     |     |     |     |
| Blood sample
DPP4 and
other
biomarkers |                 | X               | X                  |                                  |    |    |    |     |     |     |     |     |     |     |     |     |     |     |     |     |     |     |     |     |                   |     |     |     |     |     |     |     |     |
| Blood
sample for
DNA
(optional)        | X  |                 |                    |                                  |    |    |    |     |     |     |     |     |     |     |     |     |     |     |     |     |     |     |     |     |                   |     |     |     |     |     |     |     |     |

ADA = anti-drug antibodies; AE=Adverse event; ACQ-6=Asthma Control Questionnaire 6; ADA=Anti-drug antibodies; AQLQ(S)+12=Standardised Asthma Quality of Life Questionnaire for 12 Years and Older; β-HCG=Beta Human Chorionic Gonadotropin; BD=Bronchodilator; DNA=Deoxyribonucleic acid; DPP4=Dipeptidyl Peptidase-4; dECG=digital electrocardiogram; EOT =End of Treatment; ePRO=electronic Patient Reported Outcome device; FENO=Fractional Exhaled Nitric Oxide; FSH= Follicle-stimulating hormone; HIV=Human immunodeficiency virus; IgE=Immunoglobulin E; IPD= Investigational product discontinuation; nAb=Neutralizing antibodies; PK=Pharmacokinetic; PRO=Patient Reported Outcome

 Blood sample for DNA may be collected at any visit after visit 1, only after the subject has signed a separate consent.  
 UNS (Unscheduled Visit): At unscheduled visits for assessing an asthma exacerbation, the following assessments must be performed. For other unscheduled visits assessments may be performed per investigator's judgement.

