## **4.2 Treatment period**

Inclusion criteria at randomization will be confirmed at Visit 3. Before randomization the subject's compliance with their usual asthma controller ICS-LABA and other asthma controller medication, and ePRO completion must be confirmed (see section [3.1](#), inclusion criteria [18](#) and [19](#)).

Subjects confirmed as eligible will be randomized at Visit 3 (Week 0) in a 1:1 ratio (i.e. 385 subjects on tralokinumab, and 385 subjects on placebo). Subjects will be administered tralokinumab 300mg or placebo via subcutaneous injection at the study site Q2W for a total of 26 doses.

The first dose of the IP will be administered following randomization through IWRS/IVRS at Visit 3.

Following randomization the subject will receive 52 weeks of double-blind treatment, with the last dose of tralokinumab/placebo administered at Visit 28 (Week 50).

Subjects will have scheduled visits at 2-week intervals to complete protocol-specific assessments and IP administration, as listed in [Table 1](#). Restrictions as set out in section [7.7.2](#) will continue to apply throughout the treatment period. In case of an asthma worsening/exacerbation (see section [5.1.1](#)), subjects should be evaluated at the study site,

when feasible, at an unscheduled visit, or ordinary visit if the worsening happens to fall within a scheduled visit window.

Subjects will continue to measure their PEF at home, as well as record asthma symptoms and responses to questionnaires in the Asthma Daily Diary throughout the 52-week treatment period (see section 5.2.2 for details).

Subjects will have brief physical exams performed at times listed in Table 1. A complete physical exam will be performed at Visit 29 (Week 52).

Additional blood samples will be obtained from the subjects at Visits 3, 9, 16 and 29 to further explore the relationship between the clinical response of tralokinumab and biomarkers.

The subject's adherence for completing all questionnaires in the ePRO will be assessed at all visits during the treatment period, with retraining provided as required.

At Week 52 subjects will come to the site for the End of Treatment (EOT) visit. The subject should bring the ePRO device to the EOT visit and complete the ACQ-6, AQLQ(S)+12, EQ-5D-5L, and the WPAI + CIQ, unless they have been completed at home prior to the visit.

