### **5.1.6 Safety assessments**

#### **5.1.6.1 Laboratory safety assessments**

Blood and urine samples for determination of clinical chemistry, haematology, and urinalysis will be taken at visits in accordance with the schedule outlined in [Table 1](#). Haematology, Clinical chemistry, and Urinalysis samples should be collected at unscheduled visits for assessing an asthma exacerbation, at a minimum. Other unscheduled visits may be initiated as needed, and assessments performed as per investigator’s judgement. For dosing visits, all samples will be taken prior to the administration of IP.

Detailed schedules of the chemistry, haematology, and urinalysis tests are presented in [Table 2](#), [Table 3](#), [Table 4](#), and [Table 5](#), respectively.

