#### **8.4.1.2 Visit and period windows**

For the exacerbation-related analyses no windows will be applied.

For the patient reported questionnaires collected in the ePRO, the variables will be summarized based on the protocol scheduled Days with  $\pm$  3-day window.

For the other questionnaires, the window is the same as the protocol-defined visit windows. For local laboratory data, and all vital signs, the visit recorded in the WBDC system will be used.

For the central laboratory results and other endpoints that present visit-based data, the variables will be summarized based on the scheduled days with adjusted analysis-defined visit windows.

A more detailed definition of visit and period windows will be provided in the statistical analysis plan.

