#### **8.4.4.3 Laboratory variables**

Blood and urine samples for determination of clinical chemistry, haematology and urinalysis parameters will be taken at the times detailed in the CSP, and will be assessed in a central laboratory. The parameters outlined in [Table 2](#), [Table 3](#), [Table 4](#) and [Table 5](#) in Section [5.1.6.1](#), will be collected. Laboratory data will be reported in SI units.

Changes in haematology and clinical chemistry variables between baseline and each subsequent scheduled assessment will be calculated. Baseline is defined as the last available value measured prior to the first dose of randomized treatment. The change from baseline is defined as the treatment period value minus the baseline period value. There will be no imputation for missing values.

Absolute values will be compared to the relevant reference range and classified as low (below range), normal (within range or on limits) or high (above range). The AstraZeneca extended reference ranges will be used for laboratory variables (where they exist). All values (absolute and change) falling outside the reference ranges will be flagged.

Urinalysis data will be categorised as negative (0), trace or positive (+) at each time-point.

For the purposes of haematology, clinical chemistry and urinalysis shift tables, baseline will be defined as the latest non-missing assessment prior to first dose, and on-treatment will be defined as the latest non-missing assessment whilst the subject is ongoing on treatment.

For the liver function tests: AST, ALT, ALP, GGT and total bilirubin, the multiple of the AstraZeneca ULN (not extended) range will be calculated for each data point.

$$\text{Multiple} = \text{Value} / \text{ULN}$$

i.e., if the ALT value was 72 IU/L (ULN 36) then the multiple would be 2.

Subjects who meet any of the following criteria at any point during the study will be flagged:

$$\text{Multiple} = \text{Value} / \text{ULN}$$

i.e., if the ALT value was 72 IU/L (ULN 36) then the multiple would be 2.

Subjects who meet any of the following criteria at any point during the study will be flagged:

- $\text{AST} \geq 3x \text{ ULN}$
- $\text{ALT} \geq 3x \text{ ULN}$
- $\text{TBL} \geq 2x \text{ ULN}$

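### The protocol defines the laboratory shift-table value in two contradictory ways, and its worst-value laboratory displays do not exclude samples triggered by exacerbations, so they could favour tralokinumab if it reduces exacerbations

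*Protocol*

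**What the plan says.** **Sampling.** Section 5.1.6.1 of the protocol states: "Haematology, Clinical chemistry, and Urinalysis samples should be collected at unscheduled visits for assessing an asthma exacerbation, at a minimum". Footnote 15 to the study plan (Table 1) is firmer: "At unscheduled visits for assessing an asthma exacerbation, the following assessments must be performed". Tables 3 to 5 carry an unscheduled-visit column. In Table 3 every chemistry test is marked there except creatine kinase and CRP. Section 4.2 has a worsening assessed "when feasible, at an unscheduled visit, or ordinary visit if the worsening happens to fall within a scheduled visit window".

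**Shift-table value.** Section 8.4.4.3, writing about the haematology, chemistry and urinalysis shift tables, says "on-treatment will be defined as the latest non-missing assessment whilst the subject is ongoing on treatment". Section 8.5.8.2 says "The shift tables will present baseline and maximum/minimum on-treatment value, as applicable for each parameter".

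**Other worst-value displays.** Section 8.5.8.2 also plans shift plots at each subject's maximum or minimum, plots of maximum post-baseline bilirubin against maximum ALT and AST, and a count of urinalysis changes to positive at any post-baseline visit. It adds: "Frequencies of clinically noteworthy values (using AstraZeneca defined reference ranges) occurring during the clinical study will also be given".

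**Visit basis.** For central laboratory results and other visit-based data, Section 8.4.1.2 says "the variables will be summarized based on the scheduled days with adjusted analysis-defined visit windows", and then "A more detailed definition of visit and period windows will be provided in the statistical analysis plan".

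**The concern.** There are two linked problems.

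First, the last on-treatment value and the most extreme on-treatment value are different quantities. A programmer following Section 8.4.4.3 and one following Section 8.5.8.2 would produce different shift tables from the same data.

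Second, an extreme-value summary grows with the number of samples. Here that number is partly set by the primary outcome, because each exacerbation seen at an unscheduled visit adds a set of laboratory tests. One of the three exacerbation criteria is a course of systemic corticosteroids, so some of those samples may be drawn when values are disturbed. If tralokinumab works, the placebo arm has more such samples. A reader comparing arms in these displays could then credit tralokinumab with a laboratory advantage that comes only from the sampling.

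**Working it through.** **1. Check of the planning inputs (Section 8.2).** Placebo rate 0.8 per year, shape parameter k = 0.95, about 355 subject-years per arm, 37% reduction in all subjects (active rate 0.8 × 0.63 = 0.504), 1% level, taken as two-sided.

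- Variance of the log rate ratio = (1/0.8 + 1/0.504 + 2 × 0.95)/355 = 5.134/355 = 0.01446; standard error 0.1203.
- Power = Φ(0.462/0.1203 − 2.576) = Φ(1.27) = 89.7%, against a stated 90%. The inputs are used as the plan uses them.

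**2. How far sampling could differ between arms.**

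- Expected exacerbations: 355 × 0.8 = 284 on placebo and 355 × 0.504 = 179 on active. Placebo could have up to 105 more exacerbation-visit sample sets.
- Subjects with at least one exacerbation, 1 − (1 + kμ)^(−1/k): 44.8% at μ = 0.8 and 33.8% at μ = 0.504.

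**3. Which tests are most exposed (Tables 3 and 4).**

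- Calcium, chloride, CO2, glucose, phosphorus, potassium, sodium, total cholesterol and uric acid: one scheduled on-treatment sample, at Visit 29.
- Liver tests: five (Visits 5, 7, 16, 23 and 29).
- Haematology: fourteen, from Visit 4 to Visit 29.

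**4. Illustration for the nine single-sample analytes, with no drug effect on the laboratory.** Let q0 be the chance that a scheduled sample is abnormal, qe the chance for an exacerbation-visit sample, and c the share of exacerbations sampled. The documents give none of these; all are assumptions.

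P(any abnormal) = 1 − (1 − q0) × (1 + k·μ·c·qe)^(−1/k)

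| Assumption | Placebo (μ = 0.8) | Active, 37% reduction (μ = 0.504) | Gap, points |
|---|---|---|---|
| q0 = 5%, qe = 20%, c = 1 | 1 − 0.95 × 1.152^(−1/0.95) = 18.1% | 1 − 0.95 × 1.0958^(−1/0.95) = 13.7% | 4.4 |
| q0 = 5%, qe = 20%, c = 0.5 | 1 − 0.95 × 1.076^(−1/0.95) = 12.0% | 1 − 0.95 × 1.0479^(−1/0.95) = 9.6% | 2.5 |
| q0 = qe = 5%, c = 1 | 1 − 0.95 × 1.038^(−1/0.95) = 8.7% | 1 − 0.95 × 1.0239^(−1/0.95) = 7.3% | 1.3 |

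Gaps are taken before rounding. At a 50% reduction (μ = 0.4), the effect that Section 8.2 uses for the biomarker-positive population, the active figures are 12.0%, 8.7% and 6.9%, and the gaps 6.1, 3.4 and 1.8 points. With no effect on exacerbations the gap is zero in every row.

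**5. Tests with more scheduled samples.** With different assumptions (q0 = 2%, qe = 20% to 40%, c = 0.5 to 1) and a 37% reduction, the placebo excess is 2.6 to 7.4 points with one scheduled sample, 2.4 to 6.8 with five and 2.0 to 5.7 with fourteen. It shrinks as scheduled samples increase but does not vanish.

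**The case against.** **The text leans towards scheduled data.** Section 8.4.1.2 puts central laboratory results on scheduled days and leaves window detail to the SAP, which is not at hand. Sections 8.4.4 and 8.4.4.3 define change from baseline at scheduled assessments. This protects the by-visit summaries. It does not settle a maximum or minimum over the treatment period, which is not tied to a visit, and Section 8.5.8.2 states that rule without a limit. The contradiction with Section 8.4.4.3 also stands within the protocol whatever the SAP says.

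**Under the last-value rule the problem largely goes.** This is true for the shift tables, where an exacerbation sample would count only if it were the last. It does not reach the maximum/minimum shift plots, noteworthy-value frequencies, liver plots or urinalysis count.

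**Sampling during steroid use is not established.** Unscheduled visits occur only when feasible, some exacerbations are treated elsewhere, a diary alert may bring the subject in before steroids begin, and nothing times the sample. All of this stands. It is why the half-sampled and equal-risk rows are shown.

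**Safety is descriptive.** No test is distorted, but readers still compare arms in these displays.

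Some stronger readings are tempting but not supported:

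- A reader might infer that the laboratory safety comparison as a whole is biased. By-visit summaries and mean-change plots are not exposed in this way, and the bias in the rest is conditional.
- A reader might assume that every extra sample for the nine analytes comes from an exacerbation. Section 5.1.6.1 and footnote 15 also allow other unscheduled samples at the investigator's judgement.
- A reader might extend the point to vital signs. These are scheduled at nearly every treatment visit, so the single-sample problem is absent.
- A reader might conclude that real harm would be hidden. At the 37% reduction, doubling only the scheduled-visit risk on active gives 1 − 0.90 × 0.9082 = 18.3% against 18.1% on placebo. Doubling the exacerbation-visit risk as well gives 25.2% against 18.1%, which is visible. The documents do not favour either case.

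**Conclusion.** The contradiction between Sections 8.4.4.3 and 8.5.8.2 is plain from the text and rests on no assumption.

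The effect on the between-arm comparison is conditional. It needs tralokinumab to reduce exacerbations and unscheduled samples to enter the extremes. It is small unless values are also worse at exacerbation visits. When these conditions hold, the extreme-value displays favour tralokinumab with no drug effect on the laboratory. At the all-subject planning effect the illustrated gap for the nine single-sample analytes is 2.5 to 4.4 points with the assumed 20% risk at exacerbation visits, and 1.3 points if those samples are no more abnormal than scheduled ones. The abnormality risks and the share sampled are assumptions. The 37% effect is the appropriate main case because safety is summarised in all treated subjects; the 50% effect belongs to the biomarker-positive population.

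**What to change.** - Reconcile Sections 8.4.4.3 and 8.5.8.2 into one definition of the on-treatment shift-table value.
- Present the between-arm extreme-value laboratory displays (shift tables if the maximum/minimum rule is kept, shift plots, noteworthy-value frequencies, maximum liver plots and the urinalysis count) twice: on scheduled visits plus the investigational-product discontinuation visit, and on all on-treatment samples.
- Tabulate samples from unscheduled exacerbation visits separately, with the number of such samples per arm.

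The cost is a wording change and one extra set of tables. Data collection does not change, and transient extremes stay visible in the all-samples version. Showing both versions is better than dropping unscheduled values from the main tables, which would make them less sensitive to short-lived abnormalities.

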#### **8.5.8.3 dECGs**

The Investigator's assessment of the 12-lead dECG (normal or abnormal) will be listed for all subjects, along with detailing whether any abnormalities were clinically significant or not.

The number and percentage of subjects with clinically significant abnormal dECGs will be summarized by treatment group and visit.

#### **8.5.8.4 Physical Examination**

Shift tables (normal, abnormal) of baseline versus EOT will be generated, presenting the assessment for each component of the complete physical examination separately.

Listings of abnormal results will be produced.

#### **8.5.8.5 Vital Signs**

Vital signs data will be presented in the same way as described in Section 8.5.8.2 for the clinical laboratory data, and will be presented using AstraZeneca defined reference ranges, and clinically important change criteria.

All recorded vital signs data will be listed.

#### **8.5.8.6 Analysis of Immunogenicity variables**

ADA status (positive vs negative) at each visit will be summarized by treatment group. Descriptive statistics including number of subjects, mean, standard deviation, median, and range of the actual ADA titers by treatment group and visit, where possible, will be provided. The ADA status across the study for each subject will also be classified and summarized by treatment group. The association of ADA status across the study with AEs/SAEs may be evaluated. In addition, the association of ADA titers ( $\geq$  median titer in positive subjects vs.  $<$  median titer) with AE/SAEs may be evaluated for ADA-positive treated subjects only. The ADA-positive subjects across the study may also be divided into persistent positive versus transient positive. A subject will be considered as persistent positive if he/she has positive ADAs for at least two consecutive visits (with  $\geq 16$  weeks between the first and last positive value). Otherwise, the subject will be considered as transient ADA positive. The associations between ADA and AE/SAEs may be summarized for both persistent positive subjects versus transient positives subjects.

Neutralizing antibody evaluations will be conducted on confirmed ADA positive samples. The test sample is deemed positive or negative for the presence of nAb to tralokinumab relative to a pre-determined (in assay validation), statistically derived cut point.

For ADA, all subjects will be shown in the data listing.

#### **8.5.9 Analysis of pharmacokinetics**

All analyses of pharmacokinetics variables will be based on the PK data set, all analyses on Immunogenicity variables will be based on the safety analysis set.

Due to the limited sampling schedule, the PK assessment will be primarily based on the observed serum trough (predose) concentrations,  $C_{\text{trough}}$ . Empirical evaluation of potential impact of demographic covariates and ADA on  $C_{\text{trough}}$  may be conducted.

The PK data may be merged with those from other clinical studies for a population-based meta-analysis. If performed, results of the meta-analysis will be presented in a separate pharmacometrics report outside of the CSR.

